## 5.2 Exclusion Criteria

A patient will not be eligible for study participation if he/she meets any of the exclusion criteria, or will be discontinued at the discretion of the Investigator if he/she develops any of the following exclusion criteria during the study:

1. Severe hyperphosphatemia defined as serum phosphorus greater than 10.0 mg/dL on Phosphate-binders at any time point during clinical monitoring for the 3 preceding months before the screening visit.
2. Serum/plasma parathyroid hormone >1200 pg/mL. The most recent value from patients' medical records should be used.
3. Clinical signs of hypovolemia at enrollment as judged by the Investigator.
4. History of inflammatory bowel disease (IBD) or diarrhea predominant irritable bowel syndrome (IBS-D).
5. Scheduled for living donor kidney transplant, plans to change to a different method of dialysis, home HD or plans to relocate to another center during the study period.
6. Any evidence of or treatment of malignancy within one year, excluding non-melanomatous malignancies of the skin.
7. Positive serology (hepatitis C or B infection, or human immunodeficiency virus) **with** evidence of significant hepatic impairment or WBC elevation according to the Investigator.
8. History of alcohol abuse, illicit drug use, significant mental illness, or any history of drug abuse or addiction within 12 months of study enrollment.
9. Life expectancy < 12 months.
10. Use of an investigational agent within 30 days prior to Screening.
11. Previous randomization into this study.
12. Previous exposure to tenapanor
13. Involvement in the planning and/or conduct of the study (applies to both Ardelyx/CRO staff and/or staff at the study site).

14. If, in the opinion of the Investigator, the patient is unable or unwilling to fulfill the requirements of the protocol or has a condition which would render the results uninterpretable.

### 5.3 Rescreening Criteria

Rescreening will only be allowed for subjects who screen fail at Visit 1 due to serum phosphorus levels outside of the protocol inclusion range (<4.0 or >8.0 mg/dL) and based on the following criteria:

- The subject must have historical serum phosphorus >4.5 mg/dL and <7.5 mg/dL during the two months immediately prior to the original screening date.
- The subject must wait a minimum of one week prior to rescreening to ensure that they would not be off phosphate binders for a period longer than the washout period described in the protocol.

Sites must obtain Sponsor approval before rescreening a subject.

### 5.4 Patient Withdrawal

Patients are free to discontinue the study at any time, for any reason, and without prejudice to further treatment. The Investigator may remove a patient if, in the Investigator's judgment, continued participation would pose unacceptable risk to the patient or to the integrity of the study data. Some study specific discontinuation criteria will also apply to study participants receiving tenapanor or placebo:

- **Hypophosphatemia:** Serum phosphorus  $\leq 2.5$  mg/dL at any time.
- **Hyperphosphatemia:**
  - Serum phosphorus  $\geq 10.0$  mg/dL any time after Week 2 of the 26-week treatment period
  - Serum phosphorus  $\geq 9$  mg/dL for two consecutive visits after Week 2 during the 26-week treatment or safety extension period
  - Serum phosphorus  $\geq 9$  mg/dL during the randomized withdrawal period

Patients discontinued from the randomized withdrawal period will be offered the opportunity to enter the open-label safety assessment period or be discontinued from the study and return to standard of care.

Patients in the active control group, receiving sevelamer carbonate do not have specific discontinuation criteria; they will be treated based on standard of care using the package insert for guidance.

A patient who discontinues will always be asked about the reason(s) for discontinuation and the presence of any AEs. The Investigator will record the reason for early withdrawal in the eCRF.

If a patient discontinues the study, all visit procedures for Visit 23 will be completed, if possible.

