The study visits during the wash-out period for HD patients should be scheduled after the first short interval in the week to ensure data are available before a possible randomization, which could then take place after the second short interval in the week. Otherwise the randomization

visit will be scheduled the following week after the first short dialysis interval; therefore, the total length of time off phosphate binder treatment may be up to 4 weeks.

Patients who meet all inclusion/exclusion criteria will be randomized centrally 3:1 to either receive tenapanor at a dose of 30 mg bid or sevelamer carbonate based on package insert instructions (standard of care) after Visits 2, 3 or 4 (after 1, 2, or 3 weeks of wash-out) if they have a s-P level of at least 6.0 mg/dL and not more than 10.0 mg/dL and have an increase in s-P of at least 1.5 mg/dL versus pre wash-out (Visit 1, Screening Visit).

Patients randomized into the tenapanor group will receive tenapanor at a dose of 30 mg bid. Tenapanor will be taken twice daily; just prior to breakfast and dinner. Patients on HD should **not** take tenapanor at the meal immediately preceding dialysis; in this case, patients will take tenapanor prior to the next meal after dialysis. Those randomized into the active control group will take sevelamer carbonate based on standard of care using the package insert for guidance for the entire 52-week study period. Patients who are on active control will **not** have Visits 14, 16 and 18.

Investigators may decrease or increase the dose of tenapanor based on s-P levels and/or GI tolerability in 10 mg increments to a minimum of 10 mg bid or a maximum of 30 mg bid from enrollment until Day 183 (Visit 13). The dose of sevelamer carbonate may be adjusted based on standard of care for the entire 52-week study period.

During the 26-week treatment period and the safety extension period, patients on tenapanor with a s-P  $\geq 10$  mg/dL at any time after Week 2 of treatment or patients with a s-P  $\geq 9$  mg/dL for two consecutive visits after Week 2 will be discontinued and all visit procedures for Visit 23 will be completed, if possible. Patients in the active control group, receiving sevelamer carbonate do not have specific discontinuation criteria; they will be treated based on standard of care using the package insert for guidance.

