Patients who meet all the inclusion/exclusion criteria will be randomized 3:1 to either receive tenapanor at a dose of 30 mg bid or sevelamer carbonate based on package insert instructions (standard of care) after Visits 2, 3 or 4 (after 1, 2 or 3 weeks of wash-out) if they have a s-P level of at least 6.0 mg/dL and not more than 10.0 mg/dL and have an increase in s-P of at least 1.5 mg/dL versus pre wash-out (Visit 1, Screening visit).

Patients randomized into the tenapanor group will receive tenapanor at a dose of 30 mg bid. Tenapanor will be taken twice daily; just prior to breakfast and dinner. Patients on HD should **not** take tenapanor at the meal immediately preceding dialysis; in this case, patients will take tenapanor prior to the next meal after dialysis. Those randomized into the active control group will take sevelamer carbonate based on standard of care using the package insert for guidance for the entire 52-week study period. Patients who are on active control will **not** have Visits 14, 16 and 18.

Investigators may decrease or increase the dose of tenapanor based on s-P levels and/or GI tolerability. The changes must be made in 10 mg increments to a minimum of 10 mg bid or a maximum of 30 mg bid from enrollment until Day 183 (Visit 13). The dose of sevelamer carbonate may be adjusted based on standard of care for the entire 52-week study period.

During the 26-week treatment period and the safety extension period, patients on tenapanor with a s-P  $\geq$  10 mg/dL at any time after Week 2 of treatment or patients with a s-P  $\geq$  9 mg/dL for two consecutive visits after Week 2 will be discontinued and all visit procedures for Visit 23 will be completed, if possible. Patients in the active control group, receiving sevelamer carbonate do not have specific discontinuation criteria; they will be treated based on standard of care using the package insert for guidance.

At the end of the 26-week treatment period, patients in the tenapanor group only will be randomized 1:1 to either remain on the tenapanor dose they are taking on Day 183 (Visit 13) or receive placebo for up to an additional 12 weeks (randomized withdrawal period). During the randomized withdrawal period, patients with a s-P  $\geq$  9 mg/dL will be discontinued and all visit procedures for Visit 23 will be completed, if possible. Patients who discontinue from the

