##### 6.1.3.1 Discontinuation criteria

See [Section 5.4 Patient Withdrawal](#)

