### 7.3.5 Analysis of Clinical Laboratory Tests

A certified laboratory will be used to process and provide results for the clinical laboratory tests. The baseline laboratory test results for clinical assessment for a particular test will be defined as the last measurement prior to the initial dose of study drug or active control.

For any laboratory test value outside the reference range that the Investigator considers clinically significant, the Investigator will:

- Repeat the test to verify the out-of-range value.
- Follow the out-of-range value to a satisfactory clinical resolution.
- Record as an AE any laboratory test value that (1) is confirmed and the Investigator considers clinically significant, or (2) that requires a patient to be discontinued from the study, or (3) that requires a patient to receive treatment, or (4) fulfills one or more SAE criteria.

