**8.13 Unscheduled visits**

Unscheduled visits, for missed scheduled visits or safety or tolerability related reasons are allowed. Procedures performed are at the discretion of the Investigator.

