#### 8.14 Withdrawal Procedures

In the event of a patient's withdrawal, the Investigator will make every effort to complete all assessments performed at End-of-treatment visit on Day 365 (Visit 23). Withdrawn patients will be followed until resolution of any AEs or until the unresolved AEs are judged by the Investigator to have stabilized.

For the withdrawal criteria see [Section 5.4](#).

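### Section 5.4 ties the single s-P ≥10 mg/dL stop to the 26-week period, while the Synopsis and Section 4.1 also apply it in the safety extension

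*Combined protocol and SAP*

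**What the plan says.** The Synopsis (1.2) and Section 4.1 carry the same sentence. It opens "During the 26-week treatment period and the safety extension period, patients on tenapanor with a s-P" at or above 10 mg/dL and sets the timing as "at any time after Week 2 of treatment". It also stops patients with s-P ≥9 mg/dL at two visits in a row after Week 2. Both rules sit under an opening that names both periods.

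Section 5.4 lists the hyperphosphatemia stops as three bullets:

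- One value ≥10.0 mg/dL, "any time after Week 2 of the 26-week treatment period".
- Values ≥9 mg/dL "for two consecutive visits after Week 2 during the 26-week treatment or safety extension period".
- One value ≥9 mg/dL in the randomized withdrawal period.

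Section 6.1.3.1, on discontinuation criteria, contains only a pointer to "Section 5.4 Patient Withdrawal". Section 8.14 does the same: "For the withdrawal criteria see" 5.4. Sevelamer patients have no such criteria in any of these places.

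**The concern.** This is a mandatory stopping rule, and it appears to cover different periods depending on the section read. The section with the narrower wording is the one the protocol sends sites to.

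Section 2.5 counts the phosphate-related discontinuation criteria among the measures that limit severe hyperphosphatemia. With 70 to 95 sites, two sites could handle the same extension value differently, each following a section of the protocol. The only precedence rule in the text (Section 9.1) ranks the SAP over the protocol; nothing ranks 4.1 against 5.4. Section 8.16 counts noncompliance with protocol requirements as a deviation, so a site that follows 5.4 read narrowly could be recorded as departing from 4.1.

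At stake are consistent safety conduct and who is stopped in the open-label extension.

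**Working it through.** The plan gives no figure to reproduce. The check sets the texts side by side and then uses the visit days to see where they lead to different actions.

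**Step 1: periods named for each rule**

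| Place | Trigger | Periods named |
|---|---|---|
| Synopsis and 4.1 | one value ≥10 | 26-week period and safety extension |
| 5.4, first bullet | one value ≥10.0 | 26-week period |
| 5.4, second bullet | ≥9 at two consecutive visits | 26-week period or safety extension |
| 5.4, third bullet | one value ≥9 | randomized withdrawal period |

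Each 5.4 bullet names its own period or periods. The extension appears in the second bullet and not in the first, so a reader taking the three together would conclude that the single-value stop was not meant for the extension.

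**Step 2: what happens to a tenapanor patient in the extension, after Week 2**

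| s-P pattern | Synopsis and 4.1 | 5.4 read narrowly |
|---|---|---|
| one value ≥10, next visit <9 | stop at first value | no mandatory stop |
| one value ≥10, next visit ≥9 | stop at first value | stop at second value |
| two consecutive values from 9 to below 10 | stop at second value | stop at second value |
| one value from 9 to below 10, next visit <9 | no stop | no stop |

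The texts part only when a value reaches 10. In the first row the outcome differs; in the second only the timing does.

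**Step 3: length of the delay**

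Sections 8.11 and 8.12 place Visits 20, 21, 22 and 23 at Days 281, 309, 337 and 365, each ±7 days.

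- Nominal gap: 309 − 281 = 337 − 309 = 365 − 337 = 28 days.
- Shortest gap, first visit 7 days late and next 7 days early: 28 − 14 = 14 days.
- Longest gap, first visit 7 days early and next 7 days late: 28 + 14 = 42 days.

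**Step 4: where it can occur**

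For patients entering the extension at Visit 19, the scheduled visits at which the texts can differ are 20, 21 and 22. At Visit 23 no drug is dispensed, so the difference has no effect. Patients may enter earlier (Schedule of Events, footnote g), but no visit schedule is given for them.

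**Step 5: reach into the primary analysis**

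The primary endpoint is measured in the randomized withdrawal period, which has its own single-value stop at ≥9 mg/dL. The Synopsis, 4.1 and 5.4 state that stop consistently, so the mismatch does not touch the primary comparison.

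**The case against.** The best defence is grammatical. In the first 5.4 bullet, the reference to the 26-week period may only identify which Week 2 is meant, with no end point after it. The second bullet uses a word of duration and the first does not. Read this way, the stop runs on into the extension and agrees with 4.1. That reading is possible, which is why the point is ambiguity at the least. It is the weaker reading beside a bullet that names the extension outright.

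A reader might go further and infer that 5.4 tells sites to keep such patients on drug. It does not. Its list is introduced as some of the criteria that apply, the investigator may remove any patient judged to be at unacceptable risk, and 4.1 still requires the stop. The gap opens when 5.4 is used alone, which the cross-references invite.

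Other safeguards shorten the practical delay. Section 8.13 says "Unscheduled visits, for missed scheduled visits or safety or tolerability related reasons are allowed". For values the investigator considers clinically significant, Section 7.3.5 requires sites to "Repeat the test to verify the out-of-range value". Titration is allowed in the extension, and hemodialysis patients are checked at each dialysis session. These soften the consequence, but they depend on judgment and do not give all sites one rule.

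A reader might also infer that patients returning to tenapanor after placebo would be stopped before the drug has acted, and so need a two-week exemption. The documents do not support that. They give no onset time after restart, the first 5.4 bullet ties Week 2 to the 26-week period, and no exemption appears anywhere. An exemption would also loosen the stop in 4.1. What stands is a narrower question: whether Week 2 starts again for these patients is not stated clearly across the sections.

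**Conclusion.** The mismatch is real. The Synopsis and 4.1 apply the single-value ≥10 mg/dL stop in the extension; 5.4 on its plainer reading does not, and on its most generous reading is unclear. For a patient entering at Visit 19, the effect is confined to Visits 20 to 22. It is either a stop delayed by a nominal 28 days (14 to 42) or no mandatory stop if the next value is below 9. The delay assumes that no unscheduled visit, repeat test or investigator decision comes first.

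This is a minor correction to safety conduct that is worth making because the rule is mandatory and 5.4 is its reference section. Two larger inferences should be resisted. The first is that efficacy inference is at risk: the primary analysis, power and alpha are unaffected. The second is that a number of mishandled patients can be given: the documents contain no rate of isolated values ≥10 in the extension, so any count would rest on an invented rate.

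**What to change.** Reword the first hyperphosphatemia bullet in 5.4 so that it covers s-P ≥10.0 mg/dL at any time after Week 2, in the 26-week treatment period or in the safety extension. That brings it into line with the Synopsis, 4.1 and the bullet below it.

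In the same amendment, the sponsor could state whether Week 2 restarts for a patient who resumes tenapanor after placebo. The answer should cover both the ≥10 rule and the two-visit ≥9 rule, since the same doubt affects each.

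The cost is wording in an amendment and a note to sites, with no extra patients, visits or samples. The downside is slightly more discontinuations in the extension than under 5.4 read narrowly; compared with 4.1 as written, nothing changes.

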At the end of the 26-week treatment period, patients in the tenapanor group only will be randomized 1:1 to either remain on the tenapanor dose they are taking on Day 183 (Visit 13) or receive placebo for up to an additional 12 weeks (randomized withdrawal period). During the randomized withdrawal period, patients with a s-P  $\geq 9$  mg/dL will be discontinued and all visit procedures for Visit 23 will be completed, if possible. Patients who discontinue from the randomized withdrawal period with s-P  $\geq 9$  mg/dL will be offered the opportunity to enter the safety extension period. In addition, patients who randomize into the

tenapanor group and complete the randomized withdrawal period are eligible to enroll in the open label safety extension period for an additional 14 weeks. Patients who enroll into the open label extension period will receive tenapanor.

Laboratory efficacy endpoints will be assessed at designated visits throughout the study; s-P will be measured at every visit.

Safety assessments will be performed during the study and will include physical examinations, vital signs (blood pressure and pulse), body weights, clinical laboratory evaluations, 12-lead electrocardiograms (ECGs), and adverse event (AE) monitoring

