- Safety extension period: Starting dose is the same dose from the end of the 26-week treatment period. Titration is allowed as described for the 26-week treatment period.

Sevelamer carbonate (active control) will be administered PO based on standard of care during the entire 52-week study period.

Placebo will be administered PO during the randomized withdrawal period only. During this period, patients will be randomized 1:1 to receive either placebo or tenapanor. The placebo group will receive the

same number of tablets as the last dose of tenapanor they received during the 26-week treatment period. Patients from the active control group will not enter the randomized withdrawal period; they will continue to receive sevelamer carbonate per standard of care for all 52 weeks.

A detailed description of the dose adjustment procedures can be found in [Section 6.1.3](#).

**Statistical  
Analyses:**

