- d AEs and SAEs will be collected from consenting to the end of study.
- e Kt/V should be the most recent historical value prior to screening.
- f Height will also be measured at the screening visit
- g In the randomized withdrawal period, patients in the tenapanor group only are randomized 1:1 to either stay on current treatment of tenapanor or receive a matched placebo; based on withdrawal criteria, patients may enter the safety assessment period at any visit.
- h If the laboratory evaluations from the wash-out period deem the patient ineligible for the study, the site must inform the patient and tell them to take their phosphate binders.
- i s-Phosphorus sample collected at visits when safety labs are not collected.
- j KDQoL (KDQoL™-36), Kidney Disease and Quality of Life survey. DSI, Dialysis Symptom Index survey is for English speakers only and is not validated in other languages.
- k Randomization #1 is 3:1, tenapanor: active control. Randomization #2 is 1:1 from the tenapanor group only to tenapanor: placebo. Patients in the active control group will receive sevelamer carbonate for the entire 52-week study period.
- l Drug accountability will be performed for both tenapanor and the active control.
- m Visits 14, 16 and 18 are not done for subjects randomized into the active control group.
- n Patients should be randomized by the week after meeting s-P washout criteria; total period off binder must not be greater than 4 weeks.

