randomized withdrawal period with s-P  $\geq$  9 mg/dL will be offered the opportunity to enter the safety extension period.

Patients who randomize into the tenapanor group and complete the randomized withdrawal period are eligible to enroll in the open label safety extension period for an additional 14 weeks. Patients who enroll in the open label safety period will receive tenapanor during this period.

Laboratory efficacy endpoints will be assessed at various times throughout the study; s-P will be measured at every visit.

Safety assessments will be performed during the study and will include physical examination, vital signs (BP/P), body weights, clinical laboratory evaluations, 12-lead electrocardiograms (ECGs), and adverse event (AE) monitoring. Blood samples will be collected and stored, as appropriate, for the potential evaluation of exploratory biomarkers related to cardio-renal disease or bone metabolism or that may influence the response (i.e. distribution, safety, tolerability, and efficacy) to tenapanor.

Details of study assessments and the schedule of events for this study are in [Section 1.3](#).

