#### 4.1.1 Treatments Administered

At randomization (Visit 5), patients will be randomized to either tenapanor or the active control group. Patients randomized into the active control group will receive sevelamer carbonate for the entire 52-week study period. Dose of sevelamer will be adjusted per standard of care using the package insert for guidance.

Patients randomized into the tenapanor group will receive tenapanor at a dose of 30 mg bid. Tenapanor will be taken twice daily; just prior to breakfast and dinner. Tenapanor is supplied as 10 mg tablets; each dose of one to three tablets bid will achieve total daily doses of 20, 40, or 60 mg tenapanor.

The dose of tenapanor may be down titrated or up titrated to a max of 30 mg bid in a step-wise fashion based on serum-phosphorus levels and/or GI tolerability (detailed in [Section 6.1.3](#)). Down-titration can go from 30 mg bid to 20 mg bid and 20 mg bid to 10 mg bid. Dose escalation can go in 10 mg bid increments to a maximum dose of 30 mg bid.

On dialysis days, patients on HD should **not** take study drug at the meal prior to dialysis and instead take it before another meal. If a meal is skipped, the dose should be taken with another meal during the day or at around the time that the meal would have been consumed. Active control (sevelamer carbonate) will be taken based on standard of care using the package insert for guidance.

During the randomized withdrawal period, patients in the tenapanor group only will be randomized to either remain on their current dose of tenapanor or receive placebo in a 1:1 ratio.

Placebo will be administered PO during the randomized withdrawal period only for patients randomized into placebo from the tenapanor group. The same number of tablets as the last dose of tenapanor during 26-week treatment period will be administered to the placebo group. Patients from the active control group will not enter the randomized withdrawal period; they will continue to receive sevelamer carbonate per standard of care for the entire 52-week study period.

During the safety extension period, patients on tenapanor will continue at their same dose. Patients on placebo will continue with their same dose from the end of the 26-week treatment period. Titration is allowed as described for the 26-week treatment period.

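### Section 5.4 offers open-label tenapanor after any stop in the withdrawal period, including one for s-P ≤2.5 mg/dL; the synopsis and Section 4.1 do not address that case

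*Combined protocol and SAP*

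**What the plan says.** **Section 5.4 (Patient Withdrawal).** "Some study specific discontinuation criteria will also apply to study participants receiving tenapanor or placebo". The list that follows has a low limit (s-P ≤2.5 mg/dL at any time) and high limits, including ≥9 mg/dL in the randomized withdrawal period. The next paragraph reads "Patients discontinued from the randomized withdrawal period will be offered the opportunity to enter the open-label safety assessment period" and continues "or be discontinued from the study and return to standard of care". The offer carries no s-P condition.

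**Synopsis and Section 4.1.** The synopsis describes "Patients who discontinue from the randomized withdrawal period with s-P" at or above 9 mg/dL as the group who get the offer. Section 4.1 says the same: a stop at or above "9 mg/dL will be offered the opportunity to enter the safety extension period". The only other route in either place is completion of the withdrawal period. Neither says what follows a stop at ≤2.5.

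**Schedule of Events, footnote g.** "based on withdrawal criteria, patients may enter the safety assessment period at any visit". No threshold is named.

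**Dose in the extension.** The synopsis, under dose and route of administration, says: "Starting dose is the same dose from the end of the 26-week treatment period". Section 4.1.1 adds: "Patients on placebo will continue with their same dose from the end of the 26-week treatment period". Section 6.1.2 repeats the rule, and titration is allowed afterwards. Everyone who enters the extension from the withdrawal period receives tenapanor.

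**The concern.** After a high value, moving to open-label tenapanor is a rescue. After a low value, it offers a phosphorus-lowering drug to a patient who has just been stopped for low phosphorus. For a patient in the tenapanor arm, the starting dose would be the one on which s-P reached 2.5 or lower. The withdrawal period is double-blind (Section 6.3.2), so the investigator making the offer would not ordinarily know which arm the patient was in.

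Section 2.5 names the discontinuation criteria as one of the measures against severe hypophosphatemia. A stop followed by a restart at the same dose weakens that measure. The same low value in the 26-week period carries no extension offer, because Section 5.4 confines its offer to the withdrawal period.

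Sites also lack a rule for settling the question. Section 9.1 ranks the SAP above the protocol but does not rank protocol sections, and Section 11.1 bars investigators from deviating from the protocol. Two sites could handle the same result differently, each with a text to cite.

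**Working it through.** **1. The exits side by side, for a patient stopped during the withdrawal period**

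| Reason for stop | Section 5.4 | Synopsis and Section 4.1 | Footnote g |
|---|---|---|---|
| s-P ≥9 | Extension or standard of care | Extension offered | Entry possible; no threshold given |
| s-P ≤2.5 | Extension or standard of care | Not addressed | Entry possible; no threshold given |
| Other (e.g. adverse event) | Extension or standard of care | Not addressed | Unclear |

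The texts agree for ≥9. For ≤2.5, Section 5.4 makes an offer and the other two places state none.

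**2. The restart dose.** Dose is fixed during the withdrawal period at the last 26-week dose, and the extension starts at that same dose. For the tenapanor arm, the restart dose therefore equals the dose at the time of the stop.

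**3. The plan's own figures, and whether this wording enters them** (inputs from Section 9.2)
- Patients: 560 × 3/4 = 420 on tenapanor; 420 × 0.70 = 294 reach the second randomization, 147 per arm; 294 × 0.50 = 147 responders, against 146 stated.
- Power: 1.0 / (1.6 × √(2/73)) = 3.78; 3.78 − 1.96 = 1.82; Φ(1.82) ≈ 96.5%. A noncentral t calculation gives 96.3%. The stated figure of more than 95% is reproduced.
- The exit wording is not an input to either calculation. The endpoint is the last s-P within the withdrawal period (Section 9.4.3), and the offer comes after it.

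**4. How many patients could be affected.** The documents give neither the mean nor the between-patient SD of s-P levels, so this step rests on assumptions. It simulates s-P at Visits 6 to 19 with the Section 5.4 stops applied and the placebo mean raised by the protocol's 1.0 mg/dL from Visit 14.
- With level SD 1.6 and within-patient correlation 0.5, the SD of change is 1.6 × √(2 × (1 − 0.5)) = 1.6, which matches Section 9.2. For means of 5.5 to 6.5 mg/dL, stops at ≤2.5 in Visits 14 to 19 number about 3.5 to 11 of 294 if s-P is normal, and about 0.1 to 2.3 if lognormal.
- Over a wider grid (SD 1.4 to 1.8, correlation 0.3 to 0.7) the range is 0 to about 25. The top needs mean 5.5, SD 1.8, correlation 0.3 and a normal distribution. That implies a change SD of 1.8 × √(2 × 0.7) = 2.13, well above the protocol's 1.6.
- Down-titration before Visit 13 is not modelled and would lower all these counts.

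**The case against.** **The texts do not contradict each other.** Neither Section 4.1 nor the synopsis uses the word only, and Section 4.1 is a design summary. Sections 6.1.3.1 and 8.14 send the reader to Section 5.4 for the stopping criteria. Section 5.4 also leaves standard of care as an alternative. This stands: the difference is one of scope, with one text silent where the other speaks. It does not remove the problem, because the fuller text is the one that makes the unsuitable offer.

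**Leaving the study also leads to phosphorus lowering, with less monitoring.** Section 2.5 says all patients go back to their binders when participation ends. In the extension, s-P is measured at Visits 20 to 23, the dose can be reduced to 10 mg bid, the low limit still applies and the investigator may withdraw the patient. This stands in part. It limits the harm, and it is why the fix leaves binder restart to the physician. It does not justify a default restart at the unchanged dose.

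**A simulated repeat rate does not show harm from the offer.** In the middle scenario (mean 6.0, SD 1.6, correlation 0.5), a tenapanor patient restarted after a low stop has a 17% (normal) or 8% (lognormal) chance of another value ≤2.5 by Visit 23, against 2% or 0% in tenapanor patients without a stop. That compares patients selected for a low value with patients who were not. It does not compare tenapanor with a return to binders. The objection stands, and the verdict does not use these figures.

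**A reader might infer a second conflict at Visit 13**, where one visit ends the 26-week period and hosts the second randomization. The documents largely settle this. The schedule lists the Visit 13 s-P in the 26-week table and not under Visit 13 in the withdrawal table, and Sections 7.4 and 9.4.3 define Visit 13 as the end of the 26 weeks. Once a high value is assigned to a period, Sections 5.4 and 4.1 give the same answer. The inference also assumes that results arrive after randomization, and the protocol does not state the turnaround.

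**Conclusion.** The inconsistency is real, can be read directly from the text, and is minor. As written, Section 5.4 offers open-label tenapanor at the previous dose to a patient stopped for s-P ≤2.5, while the synopsis and Section 4.1 say nothing about that patient. That the offer exists and at what dose it starts needs no assumption. The number of patients does: about 0 to 11 of 294 on assumptions consistent with the protocol's SD of change, and possibly near zero.

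A reader might go further and infer that Section 4.1 forbids what Section 5.4 permits, or that the offer biases the trial. The documents support neither. Section 4.1 is silent on low stops. The primary endpoint is taken within the withdrawal period, before any offer, so the endpoint, power and between-arm comparison are unaffected. What is affected is the handling of a few patients and, slightly, who contributes extension safety data.

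**What to change.** Put the same two statements in Section 5.4, Section 4.1, the synopsis and footnote g:

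1. A patient stopped in the withdrawal period for s-P ≤2.5 mg/dL is not offered the extension and returns to standard of care, with the timing of any binder restart left to the treating physician. Section 2.5 needs a matching qualification, since it now says that all patients restart binders.
2. Patients discontinued from the withdrawal period for other reasons keep the choice Section 5.4 gives them.

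The offer should not be narrowed to s-P ≥9. That would also take it from patients who stop for an adverse event or with a rising value below 9, and would lose 52-week safety data that serve a primary objective. No Visit 13 rule should be added: reclassifying patients already randomized as 26-week discontinuations could blur who belongs in the efficacy analysis set, which requires completion of that period (Section 9.3).

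The cost is a short amendment and a note to sites, with no new visit and no change to randomization or analysis. The downside is that the few patients stopped at ≤2.5 contribute no extension exposure.
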